#### ＜相互作用＞

##### ＜併用禁忌＞（併用しないこと）

LenSx® 眼科用レーザー手術装置用でないアクセサリ類は使用しないこと。[システムの性能に影響を与え、患者に危害を与えるおそれがある。]

#### ＜不具合・有害事象＞

##### \*[有害事象]

- 白内障手術の場合
  - 後囊破損
  - 前囊切開、水晶体分割及び角膜切開の偏位
  - 不完全な前囊切開、水晶体分割及び角膜切開処置又は中断
  - 前囊の亀裂
  - 角膜擦過傷又は角膜上皮欠損
  - 眼痛
  - 感染症
  - 出血
  - 眼球組織への損傷
  - 房水漏出、前房消失
  - 眼圧上昇
- 角膜フラップ作製又は層状切除の場合
  - 角膜浮腫
  - 角膜疼痛
  - 角膜上皮増殖
  - 角膜上皮欠損
  - 感染
  - フラップの偏位
  - フラップ形成不全
  - フラップ裂傷又は不完全なリフトオフ
  - フリーキャップ

#### 【臨床成績】

白内障患者を対象として米国にて臨床試験を1試験実施した。白内障手術手技のうち、前囊切開、水晶体分割、角膜切開について、片眼は本装置を用いて（レーザー群）、対側眼は従来の手技を用いて（マニュアル群）手術を実施した。なお、本試験で用いた本装置の各設定値の範囲は、前囊切開の切開径4.2～5 mm、水晶体分割の分割数はチョップパターン2～3（切開径4.2～4.7mm）、シリンダーパターン1～4（切開径2.5～4.5mm）、水晶体分割のオフセット値は前房側500 $\mu$ m、後房側800 $\mu$ mであった。白内障手術を受けた65例がITT解析の対象となった。レーザー群の65例全例においてSoftFit患者インターフェースの圧平が成功した。レーザー群65例のうち64例に本装置による前囊切開、水晶体分割を実施し、全例が前囊切開と水晶体分割の完全例であった。また、レーザー群の65例に本装置を用いた角膜切開を実施し、メイン創口切開とサイドポート切開で部分的にブレードによる切開が必要となったそれぞれ4例（6.2%）を除いて、いずれも完全例であった。

本装置による前囊切開の真円度は、レーザー群で $0.8978 \pm 0.0048$  (平均値  $\pm$  標準偏差, 以下同様)、マニュアル群で $0.8875 \pm 0.0079$  であり、マニュアル群と比較して平均値、標準偏差ともに差がみられた (対応のある t 検定  $p < 0.0001$ , Pitman の検定  $p = 0.0004$ )。一方、前囊切開のサイズは 5mm の設定に対して、レーザー群で $4.9780 \pm 0.1909$ mm、マニュアル群で $4.9828 \pm 0.4624$ mm であり平均値に差 (対応のある t 検定  $p = 0.7160$ ) は認められなかったが、レーザー群の標準偏差はマニュアル群に比し小さかった (Pitman の検定  $p < 0.0001$ )。

白内障のグレード別の超音波時間は、白内障のグレードが「硬い」でレーザー群が $40.5 \pm 26.1$ 秒、マニュアル群で $50.8 \pm 13.1$ 秒であり大きな差が認められた (対応のある t 検定  $p = 0.0140$ )。また、白内障のグレード別の CDE では、「中等度」でレーザー群が $6.170 \pm 2.757$ 、マニュアル群で $7.242 \pm 2.159$ であり、「硬い」でレーザー群が $8.666 \pm 5.119$ 、マニュアル群が $10.749 \pm 4.487$ であり大きな差が認められた (対応のある t 検定  $p = 0.0378$ ,  $p = 0.0194$ )。

臨床試験で確認されたもっとも浅い前房深度は 2.53mm であった。

なお、本装置との因果関係が否定できない有害事象及び不具合は認められなかった。

#### 【保管方法及び有効期間等】

保管方法に関しては取扱説明書を参照すること。

#### 【保守・点検に係る事項】

1. 保守・点検に関する詳細は、本装置の取扱説明書に従うこと。
2. 弊社のサービス担当者による保守サービスを 6 ヶ月に 1 回実施する。

#### 【製造販売業者及び製造業者の氏名又は名称等】

##### 【製造販売元】

日本アルコン株式会社

#### \*【製造元】

Alcon Research, Ltd 及び Alcon LenSx Inc. アメリカ合衆国

## Appendix C Selection of Surgeon

[figure not shown]
[figure not shown]
Regarding combination of LenSx and Centurion (hereafter called LenSx group) and conventional cataract surgery (hereafter called Conventional group), the surgeons of this study surgery will be decided as follows.

Surgeon A and Surgeon B should be the same person respectively for all surgery of this study.

Group	Surgical Procedure	Surgeon
LenSx	Anterior capsulotomy and lens fragmentation by LenSx	Surgeon A
	Surgical procedure after the above mentioned procedure	Surgeon B
Conventional	All of the surgical procedure	Surgeon B

## Appendix D Emery-Little Classification

The lens condition will be graded according to the following Emery-Little classification. More than two people different from the surgeon will classify the lens condition of each patients.

Grade 1	Grade 2	Grade 3	Grade 4	Grade 5
Transparent or milky white	White	Yellow	Amber	Brown or black
				

Reference : 大鹿哲郎 編集『眼手術学 5. 白内障』 P.15, 株式会社 文光堂, 2012

**Job Notes:**

This is the first revision (Version 2.0) Statistical Analysis Plan for this study. The primary purpose of this revision was to add Modified Full Analysis Set to Efficacy Analysis Sets in Section 2.1. See Section 10, Revision History, for more detail and the other changes.

## **Executive Summary:**

### Key Objectives:

The primary objective of this study is to demonstrate less Cumulative Dissipated Energy (CDE), lower endothelial cell loss and lower average torsional amplitude with combination of LenSx® and Centurion® (LenSx) than conventional cataract surgery (Conventional).

### Decision Criteria for Study Success:

#### Primary Efficacy

Superiority of LenSx to Conventional surgery for Cumulative Dissipated Energy (CDE) at Visit 00 will be demonstrated when a treatment difference is statistically significant (one-sided alpha = 0.025, t-test).

#### Secondary Efficacy

If and only if superiority of CDE is demonstrated, hypothesis testing of superiority for Endothelial Cell Density (ECD) followed by average torsional amplitude will be conducted sequentially.

# **1 Study Objectives and Design**

## **1.1 Study Objectives**

The objective of this study is to demonstrate less Cumulative Dissipated Energy (CDE), lower endothelial cell loss and lower average torsional amplitude with combination of LenSx® and Centurion® (LenSx) than conventional cataract surgery (Conventional).

## **1.2 Study Description**

This is a prospective, observer-masked (specular microscope only), randomized, within-subject control, single-center study. The population is patients undergoing cataract surgery by phacoemulsification whose cataract grade is diagnosed as grade 2, 3 or 4 (Emery-Little classification). One eye will be assigned to Cataract surgery with LenSx and the other eye to conventional cataract surgery randomly according to the randomization list. The randomization information will be masked only to the specular microscope observer. Examinations and observations will be performed prospectively from preoperative visit until around 6 months after surgery. As 50 subjects are required for the effectiveness assessment in this study, 55 subjects will be enrolled assuming around ten percent discontinuation.

## **1.3 Randomization**

Cataract surgery with LenSx (LenSx) or conventional cataract surgery (Conventional) will be allocated to either eye within a subject according to the randomization list. The eye with more aggravated cataract will be operated first. If both eyes are the same, then always pick the right eye.

## **1.4 Masking**

This is an observer-masked study, and the only specular microscope observer will be masked with regard to treatment assignment while the study is in progress. A person different from the surgeon will be assigned as the specular microscope observer before the start of the study.

## **1.5 Interim Analysis**

No interim analyses are planned for this study.

## **2 Analysis Sets**

### **2.1 Efficacy Analysis Sets**

#### Full Analysis Set (FAS)

The FAS will include eyes with successful cataract surgery for which anterior capsulotomy and lens fragmentation have been completed using the assigned surgical techniques.

#### Modified Full Analysis Set (MFAS)

The MFAS will include eyes with successful cataract surgery for which anterior capsulotomy and lens fragmentation have been completed. Eyes will be analyzed according to the actually assigned surgical techniques. This dataset is used only for sensitivity analysis of primary and secondary endpoints.

#### Per Protocol Set (PPS)

The PPS will include all eyes with successful cataract surgery for which anterior capsulotomy and lens fragmentation have been completed using the assigned surgical techniques and meeting the following conditions;

- at least 1 postoperative visit; and
- no major protocol violation.

The PPS might exclude visits by individual subjects or observed data that do not meet the clinical study protocol criteria.

The FAS will be used for primary effectiveness analysis, secondary effectiveness analysis

████████████████████ The MFAS and PPS will be used only for sensitivity analysis of primary and secondary endpoints.

### **2.2 Safety Analysis Set**

The Pre-Treatment Safety Analysis Set will be the set that will be used to summarize occurrence of adverse experiences prior to exposure to cataract surgery using test device. The Treatment-Emergent Safety Analysis Set will be used for safety analysis after cataract surgery using test device.

## 2.3 Pharmacokinetic Analysis Set

Not Applicable.

## 3 Subject Characteristics and Study Conduct Summaries

For all analysis datasets (Safety Analysis Set, FAS and PPS), demographics (sex, age, cataract grade) will be summarized. For sex and cataract grade, the N and percentage will be summarized. For age (<60, 60-69, 70-79, ≥ 80), the N and percentage, and descriptive statistics (arithmetic mean, standard deviation, N, median, minimum and maximum) will be summarized. Study conduct summaries will be presented in a subject disposition table for all enrolled subjects.

## 4 Efficacy Analysis Strategy

The objective of this study is to demonstrate superiority of less-invasiveness of cataract surgery with LenSx to conventional cataract surgery.

### 4.1 Efficacy Endpoints

The primary endpoint is Cumulative Dissipated Energy (CDE) at Visit 00 (surgery day).

The secondary endpoints are as follows.

- Percent change of corneal endothelial cell density (ECD) at Visit 5 (150-210 days after surgery) from Pre-Operative Visit
- Average torsional amplitude (%) at Visit 00 (surgery day)

[Redacted]

- [Redacted]
- [Redacted]
- [Redacted]
- [Redacted]
- [Redacted]
- [Redacted]

█ [REDACTED]

█ [REDACTED]

█ [REDACTED]

█ [REDACTED] n

### 4.2 Efficacy Hypotheses

The null hypothesis (H0) and the alternative hypothesis (H1) for the primary analysis are as follows.

$$H_0 : \mu_{(LenSx)} = \mu_{(Conv)}$$

$$H_1 : \mu_{(LenSx)} < \mu_{(Conv)}$$

, where each of  $\mu_{(LenSx)}$  and  $\mu_{(Conv)}$  denotes the population mean of CDE for LenSx and Conventional surgery.

The null hypothesis (H0) and the alternative hypothesis (H1) for the secondary analysis are as follows.

Percent ECD change at Visit 5

Average torsional amplitude at Visit 00

$$H_0 : \mu_{(LenSx)} = \mu_{(Conv)}$$

$$H_0 : \mu_{(LenSx)} = \mu_{(Conv)}$$

$$H_1 : \mu_{(LenSx)} > \mu_{(Conv)}$$

$$H_1 : \mu_{(LenSx)} < \mu_{(Conv)}$$

, where each  $\mu_{(LenSx)}$  and  $\mu_{(Conv)}$  denotes the means of the parameters for LenSx and Conventional surgery in population.

### 4.3 Statistical Methods for Efficacy Analyses

The superiority of LenSx to Conventional surgery will be tested if there is a significant difference in mean between the surgical techniques (MMRM-based t-test, significance level: one-sided 2.5%). The descriptive statistics of CDE at Visit 00 (surgery day) will be calculated by each surgical techniques (arithmetic mean, standard deviation, N, median, minimum and maximum) and the means will be estimated using 95% confidence intervals based on the MMRM (mixed model for repeated measures).

The hypothesis on percent ECD change from preoperative visit to Visit 5 (150-210 days after surgery) will be tested only if the superiority is demonstrated in the primary analysis. The

hypothesis on average torsional amplitude at Visit 00 (surgery day) will be tested only if there is a significant difference in percent ECD change (both MMRM-based t-test, significance level: one-sided 2.5%). The descriptive statistics of ECD, absolute and percent ECD change and average torsional amplitude will be calculated for each of the surgical techniques (arithmetic mean, standard deviation, N, median, minimum and maximum) and the means will be estimated using 95% confidence intervals based on the MMRM (mixed model for repeated measures). The following is the SAS psuedo code for the primary and secondary analyses.

```
PROC MIXED ;
  CLASS surgery subjid ;
  MODEL y = surgery / DDFM=KR ;
  RANDOM subjid ;
  LSMEANS surgery / CL DIFFS ;
RUN ;
```

[figure not shown]

Table. 4–1 summarizes the key efficacy analyses.

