### 4.3 Exclusion Criteria

Exclusion criteria (Prior to Surgery)

Patients meeting any of the following 1)-16).

- 1) Corneal opacity that would interfere with the laser beam
- 2) Hypotony or the presence of a corneal implant
- 3) Residual, recurrent, active ocular or eyelid disease, including any corneal abnormality (for example, recurrent corneal erosion, etc.)
- 4) Corneal disease that precludes appplanation of the cornea or transmission of laser light at 1030 nm wavelength
- 5) Descemetocoele with impending corneal rupture
- 6) Presence of blood or other material in the anterior chamber
- 7) Poorly dilating pupil, such that the iris is not peripheral to the intended diameter for the capsulotomy
- 8) Conditions which would cause inadequate clearance between the intended capsulotomy depth and the endothelium
- 9) Any contraindication to cataract
- 10) Corneal endothelial cell density is less than 2000 cells/mm^2
- 11) Presence of peripheral iridotomy
- 12) Patients whose cataract grade of both eyes are two different levels
- 13) Pregnancy current or planned during the course of the study
- 14) Any subject currently participating in another investigational drug or device study that may confound the results of this investigation
- 15) Subjects who are expected to require an ocular surgical treatment at any time during the study

(other than Nd:YAG capsulotomy)

- 16) Disqualified by the investigator or the sub investigator because of systemic or ophthalmic diseases

[Rationale for the exclusion criteria]

1)-9): contraindication/prohibition of the test device

10) and 11): To avoid factors potentially affecting the secondary efficacy endpoints

12): To avoid the risk of creating a difference in background of both groups

The other criteria were established for general safety consideration.

Exclusion criteria (During Surgery)

Patients whose study eye meets any of the following 1)-6).

- 1) Eyes with any other additional procedures during the cataract surgery and IOL implant due to intraoperative complications that required further intervention (including but not limited to posterior capture rupture, vitreous loss, etc.)
- 2) Incomplete CCC by LenSx
- 3) Significant anterior chamber bleeding
- 4) Uncontrolled intraocular pressure
- 5) Bag-sulcus, sulcus-sulcus or unknown placement of the haptics
- 6) Disqualified by the investigator or the sub investigator because of any clinical reason (adverse event etc.)

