## 6.2 Method of Subject Selection

Subjects will be selected will be following method.

Figure 6-1 Outline of This Study

- 1) After explanation of the content of study to subject, obtain consent to participate in the clinical study from subject.

 The person in charge of randomization will prepare a randomization table using the permuted block method.

 A person different from the surgeon will be designated as the specular microscope observer before the start of the study. Specular microscope will be observed by a single observer. The specular microscope observer will assure that masking was maintained by signing the “confirmation of masking” after the end of the study.

- 2) Subject code will be assigned after obtain consent.
- 3) Perform examinations/observations (screening tests) necessary for the investigator etc. to assess eligibility according to the inclusion/exclusion criteria and the investigator will assess the qualification.
- 4) For qualified subjects, LenSx group or Conventional group will be allocated to either eye according to the randomization table.
- 5) Perform cataract surgery.  
The eye with more aggravated cataract will be operated first. If both eyes are the same, then always pick the right eye. Subjects will be assessed according to the intraoperative exclusion criteria during the surgery.
- 6) Perform the postoperative examinations.

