### 6.4 Examinations/Observations

The following examinations/observations will be performed at Visit 0 (before surgery), Visit 00 (surgery day), Visit 1 (1 day after surgery), Visit 2 (4-10 days after surgery), Visit 3 (20-40 days after surgery), Visit 4 (60-120 days after surgery) and Visit 5 (150-210 days after surgery). The same instruments and methods should be used for all measurements at all visits in a site.

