#### 1) Visit 0 (Before surgery)

The investigator should provide an adequate explanation to subjects on this study to obtain written voluntary consent from them. Each subject who has provided consent will be given a subject ID code and assessed according to the inclusion/exclusion criteria.

After consent, the following examinations/observations will be performed. Results of general examinations performed for cataract surgery before consent may be adopted as clinical study data if they are obtained within 60 days before surgery.

- Demography  
Sex, age (at consent), ophthalmic medical history, ophthalmic surgical history, and ophthalmic complications will be investigated.
  
- Specular microscope (observer-masked)  
The central corneal endothelial cell density, [REDACTED] will be measured. These observations will be performed by the same observer masked to randomization information, who is not the surgeon.  
  
[REDACTED]  
[REDACTED]
  
- Slit lamp Examination  
The eye condition will be observed by the slit lamp microscopy. The presence or absence of clinically significant ophthalmologic findings will be recorded.  
The lens condition will be graded according to the Emery-Little classification (Appendix D).
  
- Preoperative adverse experiences  
Adverse experiences occurring from consent to before surgery will be recorded.

2) Visit 00 (Surgery day, during surgery)

Confirm the assigned surgical techniques.

- Exclusion criteria (during surgery)  
Confirm the exclusion criteria of during surgery.
  
- Femtosecond laser surgery device  
LenSx® (Alcon Japan Ltd.) will be used. The same software version of LenSx® should be used for all subjects. The parameters will be set as follows.

LENS PARAMETERS

LENS METHOD	FRAG
DIAMETER	6.0 mm
ENERGY	15.00 µJ
SPOT SEPARATION	20 µm
LAYER SEPARATION	30 µm
FRAG SIZE	200 µm

CAPSULOTOMY PARAMETERS

DIAMETER	5.5 mm
ENERGY	7.00 µJ
SPOT SEPARATION	5 µm
LAYER SEPARATION	4 µm

- Recording of surgical techniques  
The surgical techniques of anterior capsulotomy and lens fragmentation will be recorded.  
“Anterior capsulotomy”  
01 – Completed with the assigned surgical techniques  
02 – Not completed with the assigned surgical techniques  
  
“Lens fragmentation”  
01 – Completed with the assigned surgical techniques  
02 – Not completed with the assigned surgical techniques
  
- Incision making  

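### The percent ECD change model leaves out each eye's Visit 0 ECD, a covariate already collected: a missed precision gain, not an error

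*SAP*

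**What the plan says.** SAP 4.3 introduces its code with "The following is the SAS psuedo code for the primary and secondary analyses". The fixed part is "MODEL y = surgery / DDFM=KR" and the random part is "RANDOM subjid". Technique is therefore the only fixed effect for cumulative dissipated energy (CDE), percent ECD change and torsional amplitude alike.

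SAP 4.1 defines the first secondary endpoint as "Percent change of corneal endothelial cell density (ECD) at Visit 5 (150-210 days after surgery) from Pre-Operative Visit". Protocol 6.4 has "The central corneal endothelial cell density" measured at Visit 0 by a masked observer. Protocol 4.3 needs the same reading for eligibility, since it excludes patients when "Corneal endothelial cell density is less than 2000 cells/mm"². By the order of steps in Protocol 6.2, screening comes before allocation.

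No readable section adjusts for this value. Protocol 9.4.2.2 names a mixed model and no covariate. The three ECD rows of SAP Table 4-1 differ only in analysis set. SAP 4.5 offers descriptive summaries by age, sex and cataract grade. A figure that follows the SAS code in SAP 4.3 could not be read, and parts of both documents are redacted.

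**The concern.** CDE and torsional amplitude have no baseline value, so a model without covariates is natural for them. Percent ECD change is different: the Visit 0 reading is both subtracted and the denominator. A baseline read too high by chance makes the loss look larger. For example, suppose the true loss is 10% (an assumption) and the baseline is read 5% high. The observed change is 0.90/1.05 - 1 = -14.3%. The shift of 4.3 points compares with a planned treatment difference of 5.5 points.

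The random subject intercept removes only what the two eyes share. Reading error that belongs to one eye stays in the residual. The between-eye difference in Visit 0 ECD carries information about that error and is not used.

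Precision matters more here than elsewhere. Planned CDE power exceeds 0.999 at every tabulated correlation. ECD power runs from 0.688 at correlation 0 to 0.934 at 0.50, and the SAP does not commit to a value. ECD also gates torsional amplitude, so a miss on ECD ends formal testing.

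**Working it through.** **Inputs from the documents.** N = 50 pairs; difference 5.5 percentage points; common SD 11; between-eye correlation ρ = 0, 0.25, 0.50, 0.75, 0.99 (SAP 7, Protocol 9.8); one-sided α = 0.025 (SAP 4.3).

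**Step 1: reproduce Table 7-2.** For a paired t-test, SE = 11·√(2(1-ρ))/√50, noncentrality = 5.5/SE, df = 49.

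| ρ | SE | Noncentrality | Power | Table 7-2 |
|---|---|---|---|---|
| 0 | 2.200 | 2.500 | 0.688 | 0.688 |
| 0.25 | 1.905 | 2.887 | 0.808 | 0.808 |
| 0.50 | 1.556 | 3.536 | 0.934 | 0.934 |
| 0.75 | 1.100 | 5.000 | 0.998 | 0.998 |

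The table is right for an unadjusted paired comparison. With complete pairs, the SAP model equals this test when the estimated subject variance is above zero. By default that variance cannot go below zero. In simulation the bound applied in 50% of trials at ρ = 0, 24% at 0.1, 4% at 0.25 and under 0.1% at 0.5. This is why the SAP model shows about 0.71 rather than 0.688 at ρ = 0 below.

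**Step 2: what adjustment can remove.** Let R² be the share of variance in the within-pair difference of percent change that is explained by the within-pair difference in Visit 0 ECD. Adjustment multiplies the SE by √(1-R²) and costs one within-pair degree of freedom. The documents do not give R², so it must be assumed. If a baseline is read with relative error e and the true Visit 5/Visit 0 ratio is k, the percent change shifts by about -100·k·e. With per-eye SD 11, this gives

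R² ≈ [(100·k·CV_read)² / (121(1-ρ))] × [CV_read² / (CV_read² + CV_eye²)].

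The second factor reflects that true differences between the eyes dilute the signal.

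Worked case, all inputs assumed: k = 0.9, CV_read = 5%, CV_eye = 2.5%, ρ = 0.25.
- R² = [4.5²/(121 × 0.75)] × [25/(25 + 6.25)] = 0.223 × 0.80 = 0.179.
- SE = 1.905 × √0.821 = 1.727, noncentrality 3.185, df = 48, power 0.877 against 0.808.
- With CV_read = 3%: R² = 0.080 × 0.590 = 0.047, power 0.826.

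These are slightly optimistic, because they ignore chance imbalance in baseline between the two techniques.

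**Step 3: simulation of both models.** 60,000 trials per cell, 50 complete pairs, subject variance bounded at zero. Assumed: between-subject CV 10%, between-eye CV 2.5%, SD of percent change held near 11. At the bound, the SE was taken from the pooled mean square with 98 df (96 adjusted), which is an assumption about Kenward-Roger behaviour there. Entries are power of the planned model → power of the adjusted model.

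| Reading CV | ρ = 0 | ρ = 0.25 | ρ = 0.50 |
|---|---|---|---|
| 0% | 0.714 → 0.704 | 0.810 → 0.802 | 0.934 → 0.928 |
| 2% | 0.714 → 0.708 | 0.806 → 0.804 | 0.933 → 0.932 |
| 3% | 0.710 → 0.714 | 0.809 → 0.820 | 0.934 → 0.946 |
| 4% | 0.709 → 0.731 | 0.808 → 0.842 | 0.933 → 0.962 |
| 5% | 0.711 → 0.755 | 0.807 → 0.874 | 0.932 → 0.980 |
| 6% | 0.709 → 0.785 | 0.805 → 0.910 | not feasible under these inputs |

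The implied R² at ρ = 0 to 0.25 is 0.04-0.05 at CV 3%, 0.14-0.19 at 5% and 0.21-0.29 at 6%, in line with the formula. The gain is not larger at low ρ: at CV 5% it is 4.4, 6.7 and 4.7 points across the three columns.

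**Step 4: sensitivity to the between-eye CV** (change in points, ρ = 0 / 0.25).

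| Between-eye CV | Reading CV 3% | Reading CV 5% |
|---|---|---|
| 1% | +1.1 / +2.1 | +5.6 / +8.2 |
| 5% | -0.4 / -0.1 | +2.3 / +3.5 |

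**Step 5: type I error.** At ρ = 0, one-sided error is 0.027-0.029 planned and 0.026-0.028 adjusted. At ρ = 0.25 and 0.5 both are 0.024-0.026. Adjustment does not inflate it.

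**The case against.** The strongest reply is that nothing here is broken. Technique is randomised within subject, the unadjusted paired comparison is valid, Table 7-2 is correct, and the documents set no power target for ECD. All of that stands.

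The second reply is that the gain rests on assumed inputs and its sign is not certain. The documents give neither a reading error nor a baseline-outcome correlation. What they do say points towards small error: "Specular microscope will be observed by a single observer" (Protocol 6.2) and "The same instruments and methods should be used for all measurements at all visits in a site" (Protocol 6.4). This stands too, and it is why the result has to be given as a range.

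Third, the largest gains cannot occur in the upper part of Table 7-2. With independent reading error at both visits and a Visit 5/Visit 0 ratio of 0.85 to 1.0, a reading CV of 5% takes 30-41% of the variance (2 × (0.85 × 5)²/121 to 2 × 5²/121). That caps ρ at about 0.59 to 0.70. At ρ = 0.75 and above, planned power is already at least 0.998 and there is nothing to gain. This is correct: the benefit is confined to moderate and low ρ. SAP 7 assumes positive correlation, so the 0.25 and 0.50 columns are more relevant than 0.

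Finally, adjustment deals with baseline reading error only, since Visit 5 error remains, and an adjusted sensitivity row might be thought enough. But a sensitivity row adds no precision to the test that gates torsional amplitude.

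**Conclusion.** The point holds as a missed precision gain on one endpoint. The omission is clear from the code, the covariate is measured in each eye before allocation, and no readable section uses it. The planned analysis remains valid and no stated figure needs correcting.

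At a between-eye CV of 2.5% the effect on power runs from a loss of about 1 point to a gain of about 11 points, depending on the reading CV. At a between-eye CV of 5% it runs from -0.4 to +3.5 points for reading CVs of 3-5%. The case for change is the asymmetry: little to lose if baseline predicts nothing, and several points to gain if reading error is 4% or more and the eyes are otherwise alike. Confidence in the size is moderate at best, because every CV is assumed.

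**What to change.** In SAP 4.3, for percent ECD change only, prespecify

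`MODEL y = surgery ecd0_dev ecd0_mean / DDFM=KR;`

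with the random subject intercept unchanged. Here `ecd0_mean` is the subject's mean Visit 0 ECD over both eyes and `ecd0_dev` is the eye's deviation from it. Splitting the covariate keeps the within-subject and between-subject slopes apart. The mean matters only for incomplete pairs or a zero subject-variance estimate. Compute it from both Visit 0 readings even if one eye has no Visit 5 value.

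Keep the present model as a sensitivity row for ECD in SAP Table 4-1, and leave the CDE and torsional amplitude models as they are. Fix the change before database lock and before anyone sees ECD by technique; chosen later, it would be open to challenge as data-driven. If the sponsor prefers the unadjusted model, the SAP should say why.

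The cost is one model line, two derived variables and one table row, with no new data. If baseline ECD predicts nothing, the loss is about 1 point of power. Nearly all of that comes from chance baseline imbalance between eyes; the lost within-pair degree of freedom (49 to 48) accounts for about 0.04 point. Two degrees of freedom are lost (98 to 96) only when the subject variance is estimated as zero.

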## **7 Sample Size and Power Calculations**

The 50 evaluable subjects will be enrolled for this study. For CDE, treatment difference was assumed 1.9% with common standard deviation of 1.2%. The sample size was simulated in Table. 7-1 varying correlation coefficient between both eyes because intra-subject positive correlation between both eyes is assumed for endpoints in this study.

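### Optional improvement: the SAP 4.3 model could include the within-subject factor on which the allocation list is blocked (eye side or operation order), at a cost of one degree of freedom

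*SAP*

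**What the plan says.** **Allocation.** SAP 1.3 states that the two techniques "will be allocated to either eye within a subject according to the randomization list". The footnote to Protocol 6.2 adds: "The person in charge of randomization will prepare a randomization table using the permuted block method". Neither document gives the block size, or says whether the list is indexed by right/left eye or by first/second operated eye.

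**Order of surgery.** Protocol 6.2 and SAP 1.3 put the worse eye first and add a rule for ties: "If both eyes are the same, then always pick the right eye". Protocol 4.3 excludes "Patients whose cataract grade of both eyes are two different levels".

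**Model.** SAP 4.3 gives one piece of code for the primary and secondary analyses. Its fixed part is "MODEL y = surgery / DDFM=KR" and its random part is "RANDOM subjid". The test is described as "MMRM-based t-test, significance level: one-sided 2.5" per cent. Eye side and operation order do not appear in that code, in the visible part of Table 4-1, or among the baseline factors of SAP 4.5.

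**The concern.** If the list is blocked on side, side is built into the design in the way that period is built into a two-period crossover. A random subject intercept pairs the two eyes, but it cannot absorb a difference between them that runs the same way in every subject. Such a difference would be counted as noise.

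Side could carry a real difference if first and second eyes behave differently. In tied pairs the right eye always goes first, and subjects whose eyes differ in grade are excluded. Right eye and first eye may therefore often coincide.

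What is at stake is efficiency. Percent ECD change is the endpoint with limited stated power, and it must succeed before torsional amplitude can be tested.

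**Working it through.** **Inputs from the documents**
- N = 50 pairs; one-sided level 0.025.
- Percent ECD change: difference 5.5, SD 11.
- CDE: difference 1.9, SD 1.2.
- Between-eye correlation ρ from 0 to 0.99 (Protocol 9.8, SAP 7).

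**Assumptions, not in the documents**
- A right-left difference g, shown as a range.
- LenSx on the right eye in 25 subjects and on the left in 25.

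**Step 1: reproduce the plan's power.** The variance of the within-pair difference is 2·SD²·(1−ρ). Paired t-test power (noncentral t, 49 df) for ECD is:

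| ρ | Stated | Recomputed |
|---|---|---|
| 0 | 0.688 | 0.6882 |
| 0.25 | 0.808 | 0.8078 |
| 0.50 | 0.934 | 0.9339 |
| 0.75 | 0.998 | 0.9984 |

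CDE power exceeds 0.999 at every correlation, as stated. The plan's model is thus in effect the paired t-test behind its own power tables.

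**Step 2: add a side difference.** The paired difference (LenSx minus Conventional) shifts by +g when LenSx is on one side and by −g when it is on the other. With 25 of each, the shifts cancel in the mean. In the sample variance they add (50/49)·g². Hence

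SE ratio = √[1 + (50/49)·g² / (2·SD²·(1−ρ))].

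**Step 3: ECD at ρ = 0.25.** The denominator is 2·121·0.75 = 181.5.

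| g (points) | SE ratio | Power, present model | Power with side term (48 df) |
|---|---|---|---|
| 0 | 1.000 | 0.808 | 0.8075 |
| 2 | √(1 + 4.08/181.5) = 1.011 | about 0.80 | 0.8075 |
| 4 | √(1 + 16.33/181.5) = 1.044 | about 0.78 | 0.8075 |
| 6 | √(1 + 36.73/181.5) = 1.097 | about 0.75 | 0.8075 |

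Power under the present model comes from a normal estimate with unchanged true variance and a residual that follows a noncentral chi-square (noncentrality 50·g²/181.5).

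**Step 4: other correlations.** At g = 5.5 (0.5 SD), ECD power by simulation without and with the side term is:
- ρ = 0.25: 0.762 against 0.810
- ρ = 0.50: 0.898 against 0.934
- ρ = 0.75: 0.993 against 0.999

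At ρ = 0.50 and g = 5.5, the mean model SE is 1.73 and the true SD of the estimate is 1.55. The actual one-sided level is about 0.015. With the side term the SE is 1.55 and the level about 0.025.

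**Step 5: CDE at ρ = 0.50.** The denominator is 2·1.44·0.50 = 1.44. For g = 0.3, 0.6 and 1.0 the SE ratio is 1.03, 1.12 and 1.31. Power stays above 0.999 even at g = 1.2 (1 SD), so only the interval width changes.

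**Step 6: dependence on blocking.** Under simple, unblocked randomisation with g = 5.5 and ρ = 0.50, the unadjusted SE is right: mean 1.73 against a true SD of 1.74. The overstatement arises only when the allocation balances technique over the factor.

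**The case against.** The case for leaving the model alone is substantial.

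- **The blocked factor is not stated.** A reader might take it as settled that technique is blocked on right and left eye. The documents say only that permuted blocks are used and that either eye may receive either technique. If the list is indexed by operation order, order is the factor to model. This stands, and the fix allows for it.
- **No side effect is documented.** One surgeon performs phacoemulsification in every eye (Protocol Appendix C), the phaco settings are common to both groups, and percent ECD change is relative to each eye's own baseline. This stands: every g above is hypothetical, and g = 6 exceeds the assumed treatment effect of 5.5.
- **Right eye is only a proxy for first eye.** The worse eye goes first, and the right-eye rule settles ties. The documents do not say that worse means a higher Emery-Little grade, so the grade exclusion does not show that most pairs are ties. This also stands.
- **The lowest stated ECD power, 0.688, belongs to zero correlation.** The plan expects positive correlation, and the relative SE inflation is smallest at low correlation. Near zero correlation, if the software bounds the subject variance at zero, part of the loss is offset: simulated power is 0.682 rather than 0.642 at g = 5.5.

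These points limit the size of the gain. They do not remove the case for a term that reflects the allocation and costs almost nothing.

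**Conclusion.** This is a free improvement, not an error. If the blocks balance technique over side and a systematic right-left difference exists, the present model overstates the standard error and the tests are conservative. For ECD at correlation 0.25 the loss is under 1 power point at a difference of 2, about 2.5 points at 4, and about 5 to 6 points at 6. Any loss on ECD also lowers the chance of reaching the torsional amplitude test.

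A reader might infer that the planned p-values are invalid or that the primary result is at risk. The documents do not support either. In the balanced case the estimate is unbiased, type I error is not inflated, the familywise claim in SAP 4.4 stands, and CDE power remains above 0.999.

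The sizes rest on the plan's own SDs, 50 complete pairs, exact 25:25 balance and an assumed g. If g is zero, nothing is lost under the present model.

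**What to change.** State in SAP 1.3 which factor the list is blocked on: right/left eye or first/second operated eye. In SAP 4.3, prespecify that factor as a fixed effect for CDE, percent ECD change and average torsional amplitude. If it is eye side, for example:

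`CLASS surgery eye subjid; MODEL y = surgery eye / DDFM=KR;`

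with the random subject effect kept. If the list is indexed by operation order, put order in place of eye. Keep the present model as a sensitivity row in Table 4-1.

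The cost is one term and one degree of freedom. With no such difference, ECD power at correlation 0.25 moves from 0.8078 to 0.8075, and at most about 0.001 is lost. Eye is already a variable in the slit-lamp listing (SAP 5.3.3). The term should be fixed before results by technique are seen, since a later addition would be open to challenge.
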